### 8.2.3. Quality of Life Analysis

The CFQ-R will be administered at Baseline and Day  $30 \pm 7$  (two timepoints) for Stage 2 subjects. Change at the Day 30 follow-up visit from baseline in CFQ-R will be presented by domain and treatment group in [Table 38](#). For the definition of baseline, refer to Section [3.3.2](#). The CFQ-R results will be presented in [Listing 15](#). This questionnaire contains a series of questions regarding several physical health and ability domains that subjects will answer as ‘Very True’, ‘Mostly True’, ‘Somewhat True’, or ‘Not at all True’ or alternatively ‘Always’, ‘Often’, ‘Sometimes’ or ‘Never’. Each question will receive a score of 1-4 with higher scores indicating more favorable QoL outcomes. Scores will be assigned to each domain based on the sum of the question scores. The analysis for this endpoint will be the change in the overall CFQ-R score from baseline at Day 30.

The CFRSD will be collected at all visits for Stage 2 subjects. Change from baseline through the Day 30 follow-up visit in CFRSD score will be presented by treatment group in [Table 39](#). CFRSD results will be presented in [Listing 16](#). The questions on the CFRSD will be scored in a similar way to those on the CFQ-R, however there will be no domain scores, only a single aggregate score for this QoL measurement. The analysis for this endpoint will be the change in the aggregate score from the Baseline visit to the highest score achieved on Days 2 through 30.

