## 4.6. Exploratory Endpoint Variables

There will be four exploratory objectives: (1) characterize the serum and sputum PK profiles of a single dose of IV bacteriophage therapy in clinically stable CF subjects with *P. aeruginosa* in expectorated sputum, (2) change in lung function from the administration of a single dose of IV bacteriophage therapy through Day  $30 \pm 7$ , (3) characterize geographically diverse *P. aeruginosa* isolates susceptibility to bacteriophages, and (4) describe subjects' QoL before and after receiving bacteriophages. The SAP for the first exploratory objective, related to serum and sputum PK, will be provided in a separate document.

Change in lung function will be measured using FEV1. Spirometry will be performed at screening, baseline, and at follow-up visits occurring on Days 2, 5, 12, and 30.

Phage susceptibility testing (PST) will occur using a plaque assay and the liquid assay. These assays describe the proportion of *P. aeruginosa* isolates that are susceptible to each phage and to the phage cocktail. Both the plaque assay and liquid assay will be evaluated every time sputum is obtained (see schedule of study

procedures in [Table 1](#)). An isolate will be considered susceptible to phage if both the plaque assay and the liquid assay indicate susceptibility.

The CFQ-R (<https://cfqr-app.netlify.app/#/questionnaire>) is a self-administered QoL questionnaire designed to measure the impact that CF has on overall health, daily life, and perceived well-being and symptoms. The CFQ-R contains 50 items and will be administered at in-person and virtual study visits for Stage 2 subjects. The CFRSD (<https://depts.washington.edu/seaqol/CFRSD-CRISS>) is a subject reported outcome measure that is used to evaluate the effect of treatment on respiratory infection symptom severity in patients with CF and chronic respiratory infection. Quality of Life will be measured using the CFQ-R and the CFRSD. The CFQ-R will be administered at baseline and at the final follow-up visit (Day  $30 \pm 7$ ). The CFRSD will be administered at baseline and at follow-up visits occurring on Day 2, 5, 8, and 30.

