### 7.2. Protocol Deviations

A summary of subject-specific protocol deviations will be presented by the reason for the deviation, the deviation category, and treatment group for all enrolled subjects in Stage 1 in [Table 2](#), Stage 2a in [Table 3](#) and Stage 2a and 2b in [Table 4](#). All subject-specific protocol deviations and non-subject specific protocol deviations will be included in Appendix 3 as data listings ([Listing 3](#) and [Listing 4](#), respectively).

Any missing CFQ-R or CFRSD assessments will not be considered protocol deviations. If an unscheduled study visit occurs, any assessments/procedures that do not occur will not be considered protocol deviations.

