**Table 39: Change from Baseline of QoL Score, CFRSD Questionnaire – ITT Population, Stage 2a and 2b**

[Implementation note: ‘Selected Dose’ will be replaced with the dose chosen by the interim analysis.]

Time Point	Treatment Group	Total QoL Score					Change from Baseline					
		n	Mean	SD	Median	Min, Max	n	Mean	SD	Median	Min, Max	95% CI a
Baseline	Selected Dose (N=X)	x	XX.X	XX.X	XX	XX, XX	-	-	-	-	-	-
	Placebo (N=X)	x	XX.X	XX.X	XX	XX, XX	-	-	-	-	-	-
Day 2	Selected Dose (N=X)	x	XX.X	XX.X	XX	XX, XX	x	XX.X	XX.X	XX	XX, XX	X.XX, X.XX
	Placebo (N=X)	x	XX.X	XX.X	XX	XX, XX	x	XX.X	XX.X	XX	XX, XX	X.XX, X.XX
Day 5	Selected Dose (N=X)	x	XX.X	XX.X	XX	XX, XX	x	XX.X	XX.X	XX	XX, XX	X.XX, X.XX
	Placebo (N=X)	x	XX.X	XX.X	XX	XX, XX	x	XX.X	XX.X	XX	XX, XX	X.XX, X.XX
Day 8	Selected Dose (N=X)	x	XX.X	XX.X	XX	XX, XX	xx	XX.X	XX.X	XX	XX, XX	X.XX, X.XX
	Placebo (N=X)	x	XX.X	XX.X	XX	XX, XX	xx	XX.X	XX.X	XX	XX, XX	X.XX, X.XX
Day 30	Selected Dose (N=X)	x	XX.X	XX.X	XX	XX, XX	xx	XX.X	XX.X	XX	XX, XX	X.XX, X.XX
	Placebo (N=X)	x	XX.X	XX.X	XX	XX, XX	x	XX.X	XX.X	XX	XX, XX	X.XX, X.XX
Maximum	Selected Dose (N=X)	x	XX.X	XX.X	XX	XX, XX	xx	XX.X	XX.X	XX	XX, XX	X.XX, X.XX
	Placebo (N=X)	x	XX.X	XX.X	XX	XX, XX	x	XX.X	XX.X	XX	XX, XX	X.XX, X.XX

Notes: N=Number of subjects in the ITT population in Stage 2a and 2b.

n=Number of subjects in the ITT population in Stage 2a and 2b with non-missing QoL score at the time point of interest. For the change from baseline, n represents the number of subjects in the ITT population in Stage 2a and 2b with non-missing values at baseline and at the time point being assessed.

SD=Standard Deviation

Baseline is defined as the last measurement taken prior to dosing on Study Day 1.

\*95% CI is calculated from a t-distribution.

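### The named CFRSD analysis compares the highest of four later scores with one baseline score, so its within-arm interval will usually exclude zero when nothing has changed

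*SAP*

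**What the plan says.** SAP 8.2.3 (Quality of Life Analysis) sets the CFRSD analysis as the "change in the aggregate score from the Baseline visit to the highest score achieved on Days 2 through 30". SAP 4.6 gives the schedule: "The CFRSD will be administered at baseline and at follow-up visits occurring on Day 2, 5, 8, and 30". Four post-baseline scores are therefore set against one baseline score.

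The same section also says that "Change from baseline through the Day 30 follow-up visit in CFRSD score will be presented by treatment group". Table 39 accordingly has rows for baseline, Days 2, 5, 8 and 30, and Maximum, each for the selected dose and for placebo. Every change row, Maximum included, has a 95% CI column, footnoted "95% CI is calculated from a t-distribution". There is no between-arm column.

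For the other instrument the section uses one visit: "The analysis for this endpoint will be the change in the overall CFQ-R score from baseline at Day 30". On direction, it says of the CFQ-R that "Each question will receive a score of 1-4 with higher scores indicating more favorable QoL outcomes", and then that "The questions on the CFRSD will be scored in a similar way to those on the CFQ-R". It does not separately state which way the CFRSD runs.

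SAP 7.2 adds that "Any missing CFQ-R or CFRSD assessments will not be considered protocol deviations", and SAP 6.5 confines missing-data methods to DOOR.

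**The concern.** The exploratory objective is to describe quality of life before and after dosing. A maximum taken over several visits is biased upward as a measure of before/after change, because each subject's post-baseline value is selected for being high and the baseline value is not. A t interval around its mean is a valid interval for the mean of a maximum. It does not indicate whether scores moved after dosing.

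A reader who takes the named analysis at face value would see a change in both arms, with an interval clear of zero, from a product that does nothing. That would also disagree with the visit rows directly above it. If higher CFRSD scores are better, the artefact looks like improvement; on a reversed scale it looks like worsening.

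**Working it through.** The documents state no SD, error rate or sample size for the CFRSD, so there is no plan figure to reproduce. The check is what the Maximum row does when nothing has changed.

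**Inputs.** Four post-baseline scores and one baseline score (SAP 4.6 and the schedule in SAP Table 1). Arms of 20 to 25 (SAP 5). A within-arm two-sided 95% t interval (Table 39; Protocol 10.5.1). Assumed: normal within-subject errors with SD 1, no true change, all visits complete.

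**Size of the shift.** For one subject the change is max(e1, e2, e3, e4) − e0. The subject's own level cancels, so the result does not depend on an exchangeable between-visit correlation.

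- Mean of the maximum of four standard normals: 1.0294; variance 0.4917.
- SD of the change: √(1 + 0.4917) = 1.2214.
- In total-SD units the shift is 0.73, 0.56 and 0.32 at correlations 0.5, 0.7 and 0.9. The exclusion rate below is the same at each.

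**How often the interval excludes zero.** The noncentrality is 1.0294 × √n / 1.2214, which is 3.77 at n = 20 and 4.21 at n = 25. The noncentral t gives the four-visit row below, and simulation agrees. All exclusions are on the upper side.

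| Completed post-baseline visits | Mean shift (SD units) | n = 20 | n = 25 |
|---|---|---|---|
| 4 | 1.03 | 95% | 98% |
| 3 | 0.85 | 82% | 90% |
| 2 | 0.56 | 46% | 55% |
| 1 (a fixed visit) | 0 | 5% | 5% |

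**Other assumptions (simulated, n = 20).**

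- Serial correlation by visit, AR(1) 0.3 to 0.7: 92% to 86%; at 0.9, 82%.
- Bounded whole-number score on an assumed range of 8 to 32 (the item count is not in the documents), with 1% to 37% of subjects at the ceiling at baseline: 94% to 84%. A more severe ceiling brings it to 62%.
- Post-baseline scores missing at random: 81% with 20% missing, 51% with 40% missing.

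**Does the placebo column rescue it?** A Welch comparison of the maximum between arms, n = 20, no true effect:

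- Matched arms: centred on zero, 5% false positives.
- Four visits against three: shift 1.0294 − 0.8463 = 0.18 SD, 7%.
- Four visits against two: shift 1.0294 − 0.5642 = 0.47 SD, 21%.
- Equal visits, one arm's SD 1.5 times the other's: 17%.

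**Replacement measures under the same null.** Day 30 minus baseline has SD √2 = 1.41. The mean of four scores minus baseline has SD √(1 + 1/4) = 1.12. Both are centred on zero and exclude it in 5% of trials.

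**The case against.** The strongest reply is that nobody is testing this interval against zero. SAP 6.8 calls the study exploratory and plans no formal testing of the primary endpoints, SAP 8.2.3 gives no decision rule for the CFRSD, and placebo stands beside the selected dose in every row. A peak response is also a defensible summary after a single dose: DOOR itself uses the greatest reduction by Day 8, and a Day 30 measure could miss a brief early change. Maximum rows with t intervals also appear in Tables 19, 34 and 36, so this looks like a shell convention. The CFQ-R is a weak precedent, because Day 30 is its only post-baseline assessment.

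Much of this stands. The endpoint informs no dose, sample-size or DOOR decision, and the contrast with 5% matters only to a reader who interprets the interval as evidence of change. That is the natural reading, however, when the objective is before against after and this is the only CFRSD quantity named as the analysis. Tables 19, 34 and 36 differ because the text does not name their Maximum rows as the analysis. DOOR differs because it is estimated as a contrast between arms. The placebo column helps only if the arms match in variability and completed visits, and no contrast is planned. The documents do not suggest differential completion; they simply do not guard against it.

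**Conclusion.** The concern holds as an analysis choice that is wrong as written on an exploratory endpoint. Within the CFRSD analysis, the fault is limited to the sentence naming the highest score and to the Maximum row's interval; the Day 2, 5, 8 and 30 rows do not have it.

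With complete visits and independent normal errors, the row shows a spurious shift of 1.03 within-subject SDs, and its interval excludes zero in 95% to 98% of trials at 20 to 25 per arm. It still excludes zero in most trials under the serial-correlation, ceiling and random-missingness settings tried, but not at 20 per arm if only two visits are completed (46%). The error structure, score range and missingness patterns are assumptions, because the documents give no CFRSD variance or item count. Whether the artefact flatters or disfavours the product depends on the scoring direction, which the SAP leaves to inference.

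**What to change.** In SAP 8.2.3, name Day 30 minus baseline, or the mean of the Day 2 to 30 scores minus baseline, as the CFRSD analysis. In Table 39, add the between-arm difference in that measure with its 95% CI, keep the by-visit rows, and keep Maximum as a descriptive row without a within-arm interval. State which direction of the CFRSD score is favourable. If Maximum stays, also say whether early-termination and unscheduled scores count towards it, since the CFRSD is collected at those visits too.

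The cost is one sentence and a table-shell edit. A Day 30 value or a mean estimates something different from a peak and is less sensitive to a brief early change. The retained visit rows and the descriptive Maximum row would still show such a change.

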### 8.2.4. Subgroup Analyses

A subgroup analysis of the primary endpoints will be conducted to explore whether estimated treatment effects vary significantly between subcategories of trial subjects, including bacteriophage susceptibility and presence of co-infection with other organisms recovered on sputum cultures. Analysis of the difference in

mean change between IV bacteriophage and placebo arms and the  $\log_{10}$ -transformed difference in mean change, along with the corresponding 95% CIs, will be presented by subgroup in [Table 22](#). A forest plot of the differences in *P. aeruginosa* colony counts is presented by subgroup in [Figure 8](#) and a forest plot of differences in the  $\log_{10}$  *P. aeruginosa* colony counts is presented by subgroup in [Figure 9](#). Analysis of the primary DOOR endpoint at Day 8 will be presented by subgroup in [Table 29](#) and a contingency table of DOOR by subgroup, treatment group, and time point will be presented in [Table 30](#). A forest plot of DOOR probability in subgroups will be presented in [Figure 11](#).

### 8.3. Interim Analyses

The interim microbiologic activity review will consist of a quantitative evaluation of potential effect sizes and associated precision using a predicted intervals and PIPs approach. Predicted intervals for DOOR probability through Day 8 + 3 will be calculated under the following range of assumptions:

1. The trends in outcomes observed at the time of the interim analysis continue to the end of study.
2. Both DOOR distributions are identical. Null distribution of cell proportions for the DOOR of IV bacteriophage dose vs placebo, will be calculated as  $\bar{P}_i = rP_{1i} + (1 - r)P_{2i}$  ( $i = 1, \dots, D$ ), where
  - $r$  is the proportion of IV bacteriophage subjects
  - $P_1$  is the proportion of subjects in the IV bacteriophage dose group in the  $i$ th DOOR category
  - $P_2$  is the proportion of subjects in the placebo group in the  $i$ th DOOR category
  - $D$  is the number of DOOR categories
3. Best and worst-case scenarios for remaining outcomes. The best-case scenario will be assumed as DOOR = 1 for all remaining subjects in the bacteriophage group and observed placebo proportions at the time of the interim analysis for all remaining subjects in the placebo group. Worst case scenario will be assumed as DOOR = 4 for all remaining subjects in the bacteriophage group and observed placebo proportions at the time of the interim analysis for all remaining subjects in the placebo group.

These PIPs provide a prediction of the trial results were the trial to continue as planned under the above assumptions regarding future data [3]. For each assumption, 10,000 complete datasets (with  $N = 20$  subjects in each treatment group for current sample size or  $N = 25$  for increased sample size) will be simulated and used to calculate the probability of rejecting the null hypothesis for each scenario.

Similar to DOOR, changes in  $\log_{10}$  *P. aeruginosa* colony counts (total and each morphology) in sputum cultures from administration of IV bacteriophages through Day 8 + 3, will be evaluated, using PIPs to assess the precision for measuring differences in  $\log_{10}$  CFU/mL count. Predicted intervals will be calculated under a range of assumptions including:

1. The trends in outcomes observed at the time of the interim analysis continue to the end of study
2. Best case: remaining bacteriophage subjects simulated to have  $> 2 \log_{10}$  reduction in *P. aeruginosa* CFU/mL, remaining placebo subjects simulated to have the same trend observed in placebo subjects at the time of the interim analysis
3. Worst case: remaining bacteriophage subjects simulated to have  $< 1 \log_{10}$  reduction in *P. aeruginosa* CFU/mL, remaining placebo subjects simulated to have the same trend observed in placebo subjects at the time of the interim analysis

The planned total Stage 2a + Stage 2b sample size (20 subjects per treatment group) will be reevaluated after the completion of Stage 2a. If necessary, the final sample size will be increased to up to 25 subjects for the placebo arm and up to 25 subjects for the selected bacteriophage dose to provide the desired precision of estimates.

Tables, listings, and figures for the planned interim analyses will not be shown in this SAP. They will instead appear in the Phage Advisory Group Charter document.

## 9. SAFETY EVALUATION

All safety analyses will be presented using the Safety Population unless otherwise noted.

When calculating the incidence of AEs and SAEs (i.e., on a per subject basis), each subject will be counted once for their most related and/or highest severity AE reported, and any repetitions within a subject will be ignored for events coded in the same category by MedDRA. The denominators for percent values will be indicated within the table or table header and denominators will consist of the maximal size of the Safety Population in the indicated observation period.

### 9.1. Demographic and Other Baseline Characteristics

Categorical demographic variables, such as sex, ethnicity, and race, will be summarized by treatment group for the ITT population in [Table 14](#) and for the Safety Population in [Table 15](#). Ethnicity will be categorized “Hispanic or Latino,” or “Not Hispanic or Latino,” “Unknown,” or “Not Reported.” In accordance with National Institutes of Health (NIH) reporting policies, subjects may self-designate as belonging to more than one race or may refuse to identify a race, the latter reflected in the CRF as “No” to each race option. Continuous baseline variables, such as age, height, and weight, will be summarized by treatment group for the ITT population in [Table 16](#) and for the Safety Population in [Table 17](#). Individual subject listings will be presented for all demographic and baseline characteristics in [Listing 6](#).

#### 9.1.1. Prior and Concurrent Medical Conditions

All current illnesses and past pre-existing medical conditions will be MedDRA coded using the MedDRA dictionary version 25.0 or higher.

Number and percentage of subjects’ pre-existing medical conditions will be presented by the MedDRA SOC and treatment group for the ITT population in [Table 18](#).

Individual subject listings will be presented for all pre-existing and concurrent medical conditions in [Listing 7](#).

#### 9.1.2. Prior and Concomitant Medications

Prior medication is defined as any medication taken before the first date of study product or placebo administration. Concomitant medication is defined as any medication started on or after the first date of study product or placebo administration.

Summaries of medications that were started prior to dosing and continuing at the time of dosing will be coded to the Anatomical Therapeutic Classification (ATC) using the World Health Organization (WHO) Drug Dictionary. The use of prior medications will be summarized in [Table 123](#), [Table 124](#), and [Table 125](#) and concomitant medications will be summarized in [Table 126](#), [Table 127](#), and [Table 128](#), by the number and proportion of subjects in each arm and treatment group within each ATC1 and ATC2 code for the Safety Population. If a subject took a specific medication multiple times or took multiple medications within a specific therapeutic class, that subject would be counted only once for the coded drug name or therapeutic class.

A by-subject listing of prior and concomitant medication use will be presented in [Listing 25](#) and [Listing 26](#), respectively.

## 9.2. Measurements of Treatment Compliance

Dates of first treatment will be summarized by site and treatment group in [Table 9](#). Treatment administration information will be included in [Listing 8](#). A listing of infusion interruptions will be presented in [Listing 9](#). A listing of all subjects who took at least one dose of study product is provided in [Listing 1](#).

## 9.3. Adverse Events

When calculating the proportions of subjects with AEs within a given MedDRA category, subjects will be counted once for each dosing period within the same MedDRA category, and the event will be reported according to the highest severity recorded throughout the indicated time period (separately for related and unrelated AEs when both severity and relatedness are tabulated). Repeated AEs will be ignored. When calculating the number of AEs that occurred, all AEs will be summarized by treatment group, including repetitions. All reported AEs will be included in the summaries and analyses.

### 9.3.1. Treatment-Emergent Adverse Events of Grade 2 or Higher

The primary safety endpoint for this study is the number of Grade 2 or higher TEAEs through Day  $30 \pm 7$ . This endpoint will be analyzed using the ITT population and is described further in Section [8.1.1](#).

### 9.3.2. Unsolicited Adverse Events

The proportion of subjects reporting at least one unsolicited AE will be summarized by MedDRA SOC, HLT, and PT and by treatment group. Denominators for proportions are the number of subjects in the Safety Population in each treatment group.

Unsolicited AEs by subject will be presented in [Listing 17](#).

The following summaries for unsolicited AEs will be presented:

- Overall summary of AEs ([Table 40](#)).
- AEs occurring in 5% of subjects in any treatment group are summarized by MedDRA SOC, HLT, and PT and by treatment group in Stage 1 ([Table 41](#)), Stage 2a ([Table 42](#)), and Stage 2a and 2b ([Table 43](#)).
- Subject incidence and total frequency of unsolicited AEs by MedDRA SOC, HLT, and PT and by treatment group with 95% CI, calculated using an exact Clopper-Pearson confidence interval in Stage 1 ([Table 46](#)), Stage 2a ([Table 47](#)), and Stage 2a and 2b ([Table 48](#)).
- Summary of unsolicited AEs by severity, relationship to study product, MedDRA SOC, HLT, and PT and by treatment group in Stage 1 ([Table 49](#)), Stage 2a ([Table 50](#)), and Stage 2a and 2b ([Table 51](#)).
- Summary of TEAEs, on-therapy SAEs, and AEs leading to discontinuation by MedDRA PT in Stage 1 ([Table 52](#)), Stage 2a ([Table 53](#)), and Stage 2a and 2b ([Table 54](#)). TEAEs are any AEs that were not present before the first dose of study product or were present before the first dose of study product and increased in severity during the treatment period. On-therapy SAEs are any SAEs occurring during or after the infusion of bacteriophage/placebo product.
- Summary of fatal on-therapy SAEs by MedDRA PT and treatment group ([Table 55](#)).
- Bar chart frequency of AEs by severity, MedDRA SOC, and treatment group in Stage 1 ([Figure 14](#)), Stage 2a ([Figure 15](#)), and Stage 2a and 2b ([Figure 16](#)).
- Bar chart incidence of AEs by severity, MedDRA SOC, and treatment group in Stage 1 ([Figure 17](#)), Stage 2a ([Figure 18](#)), and Stage 2a and 2b ([Figure 19](#)).

